### 13.7 Confidentiality

All records identifying the subject will be kept confidential and, to the extent permitted by the applicable laws and/or regulations, will not be made publicly available.

Subject names will be kept confidential. Only the subject number and initials will be recorded in the CRF, and if the subject name appears on any other document, it must be obliterated. In cases where the local law does not allow using the subject initials serial number will be appointed (e.g. AAA, BBB). Study findings stored on a computer will be stored in accordance with local data protection laws. The subjects will be informed in writing that representatives of the sponsor, IRB or Regulatory Authorities may inspect their medical records to verify the information collected, and that all personal information made available for inspection will be handled in strictest confidence and in accordance with local data protection laws. Subjects will also be informed that information regarding the study that does not include subject identifiers will be posted on [clinicaltrials.gov](http://clinicaltrials.gov).

If the results of the trial are published, the subject's identity will remain confidential. The investigator will maintain a list to enable subjects' records to be identified.

### 13.8 Use of Data and Publications

The Medtronic-MITG Publication and Authorship Policy is aligned with the International Committee of Medical Journal Editors (ICMJE) recommendations ([www.icmje.org](http://www.icmje.org)). Medtronic will seek to publish, in appropriate peer-reviewed journals and scientific conferences, results of clinical studies where human subjects are involved, regardless of outcome. While study results are owned by Medtronic, all data on which a publication is based will be made available to all authors as required for their participation in the publication process. Furthermore, data may be published or used by study investigators provided that such publication or use is in accordance with this protocol, the Medtronic-MITG Publication and Authorship Policy, and the Clinical Investigation Agreement. Investigators must submit a copy of all manuscripts and/or abstracts to Medtronic for review and comment 30 days prior to planned submission. Medtronic acknowledges that its right to review and comment shall relate solely to the proprietary, licensing, and/or confidential rights Medtronic may have in such proposed publication, rather than whether such results and/or opinions are favorable to Medtronic.

The publication of substudies, post-hoc analyses, regional results, or single-center experiences based on multicenter clinical studies should not precede that of the primary multicenter publication, and should cite the primary publication whenever possible, as required by specific journal and scientific meeting guidelines.

Medtronic involvement in a publication (e.g., funding of the study; sponsor of the study; collection, analysis, and interpretation of data; professional writing assistance) must be disclosed according to

journal-specific policies, submission requirements, and prevailing editorial standards, in addition to those specified by ICMJE. Authors must ensure that an acknowledgement/disclosure statement is included in the body of the manuscript for Medtronic to review for accuracy. All authors must also disclose financial or personal affiliations that could be considered conflicts of interest as per journal/conference requirements.

To enable health care providers, payers, and patients access to the wealth of Medtronic's research, Medtronic will report its scientific data in accordance with the principles outlined in the Guidance Document on Registration and Reporting Results of Company-Sponsored Clinical Trials Under FDAAA 2007 (Title VIII).

#### **14.0 Monitoring Procedures**

Site visits will be conducted by an authorized Medtronic representative to inspect study data, subjects' medical records, and CRFs in accordance with appropriate FDA regulations and the respective local and national government regulations and guidelines (if applicable). The Study Investigator and the investigating site will permit authorized clinical research personnel and clinical monitors from Medtronic and/or designee(s) employed by Medtronic to review completed CRFs, IRB decisions, and Investigator, clinical site records, and facilities relevant to this study at regular intervals throughout the study per the monitoring plan. Additionally, subject charts and clinical records will be requested and reviewed so that protocol adherence and source documentation can be verified. The accuracy and quality of the data obtained from the investigator and maintained by Medtronic will be confirmed through a structured program of clinical field auditing and internal review detailed in the monitoring plan. In instances where data protection regulations prohibit the direct examination of hospital records by the study Sponsor or designee(s), the Investigator will cooperate in a system of source data verification with the Sponsor. Monitoring may be performed with in person visits or remotely, when applicable.

To ensure the rights, safety, and welfare of study subjects are being maintained, the monitor will review training records to ensure all study staff are trained on the study protocol and use of the study devices. If the monitor discovers that an investigator is not complying with the signed Investigator Agreement, the investigational plan, applicable laws, or any conditions of approval imposed by the reviewing IRB, the monitor will report to the Sponsor and take such steps necessary to promptly secure compliance. If compliance cannot be secured, device shipments to the investigator may be discontinued and the investigator's participation in the investigation terminated. The monitor shall also require such an investigator to dispose of or return the device, unless this action would jeopardize the rights, safety, or welfare of a subject.

#### **15.0 Data Collection and Processing**

This study will utilize an electronic database and eCRF. All data requested on the eCRF are considered required. Data points not collected and/or recorded will be considered deviations unless otherwise specified.

The Principal Investigator must ensure the accuracy and completeness of the recorded data and then provide his/her signature on the appropriate eCRFs. The Investigator's electronic signature for specific

eCRFs will be documented in compliance with local regulations. Changes to data previously submitted to the sponsor will require a new signature by the Investigator to acknowledge/approve the changes.

Visual and/or computer data review will be performed to identify possible data discrepancies.

In cases of polyp size measurement discrepancies between CCE/CTC and OC, a Clinical Events Committee (CEC) will adjudicate OC polyp size measurements.

Manual and/or automatic queries will be created in the Oracle remote RDC system and will be issued to the site for appropriate response. The site staff will be responsible for resolving all queries in the database.

This study will be using a 21 CFR Part 11 compliant electronic data capture system. All system level validation documentation is retained within the Information Systems group.

## **16.0 Study Supplies and Device Accountability**

### **16.1 Indication**

The PillCam® COLON 2 capsule endoscopy system is intended to provide visualization of the colon. It may be used for detection of colon polyps in patients after an incomplete optical colonoscopy with adequate preparation, and a complete evaluation of the colon was not technically possible. In addition, it is intended for detection of colon polyps in patients with evidence of gastrointestinal bleeding of lower GI origin. This applies only to patients with major risks for colonoscopy or moderate sedation, but who could tolerate colonoscopy and moderate sedation in the event a clinically significant colon abnormality was identified on capsule endoscopy.

### **16.2 Contraindications**

PillCam® COLON 2 capsule is contraindicated for use under the following conditions:

- In patients with known or suspected gastrointestinal obstruction, strictures, or fistulas based on the clinical picture or pre-ingestion testing and profile.
- In patients with cardiac pacemakers or other implanted electromedical devices.
- In patients with dysphagia or other swallowing disorders.

### **16.3 Packaging and Storage**

PillCam® COLON 2 capsule should be stored in a dry place, at a temperature below 25°C (81°F) and away from magnetic sources. To prevent capsule activation, PillCam® COLON 2 capsule should be kept in the box until use.

Even if stored in its original container and according to recommendations, PillCam® COLON 2 capsule should not be used past the expiration date.

### **16.4 Inventory Control**

The Sponsor will initiate shipment of equipment to the site upon receipt of all required documents (e.g., IRB approval, local regulatory authorities' approval if applicable). The Sponsor will maintain tracking for

all shipment documentation. Prior to any shipment, the site will be informed by the Sponsor on the upcoming shipment, expected arrival date, and content of the shipment. The site should confirm receipt of the shipment.

For each dispensed capsule, the following information should be recorded: the subject study number and the capsule ID number.

At the termination of the study, all unused study material must be returned with the corresponding documentation as directed by Medtronic.

**17.2 Retention of Records**

The investigator will maintain the records of the study including all pertinent correspondence, the study protocol with any/all amendments, all correspondence with and approval from the IRB, the clinical trial agreement, the Investigator Agreement, investigational device accountability records, individual subject records, and signed informed consent forms. Subject files and other source data must be kept for a period of not less than 2 years after the date on which this investigation is terminated or completed. All data and documents should be made available if requested by relevant authorities.

### **17.3 Study Completion/Termination of Study**

Medtronic reserves the right to discontinue the study at any stage, with suitable written notice to all investigators, all reviewing IRB, and FDA.

Similarly, investigators may withdraw from the study at any time, subject to providing written notification to Medtronic 30 days prior to the date they intend to withdraw. However, Medtronic and investigators will be bound by their obligation to complete the follow-up of subjects already participating in the study. The subjects must be followed according to the clinical protocol, and information obtained during subject follow-up shall be reported to Medtronic on the appropriate eCRF.

Any USADE will be investigated immediately and, if the sponsor determines that unreasonable risk to subjects is possible, the study will be terminated and all regulating authorities and participating investigators will be notified.

**19.0 Appendix A – CCE Procedure Instructions**

The purpose of this multicenter, prospective, randomized study is to compare the diagnostic yield, accuracy, and safety of colon capsule endoscopy (CCE) and computed tomographic colonography (CTC) in the identification of colonic polyps in a screening population.

This appendix includes instructions for the CCE randomized procedure in 4 parts:

- Appendix A1 – CCE Bowel Preparation
- Appendix A2 – CCE Subject Instructions Form
- Appendix A3 – CCE Procedure Instructions
- Appendix A4 – CCE Image Reading Instructions
- Appendix A5 – CCE Bowel Cleansing Scale

### 19.1 Appendix A1 – CCE Bowel Preparation Instructions

Subjects will be instructed to follow a detailed dietary and colon preparation regimen prior to and during the CCE procedure day. With the exception of Gastrografin, all colon preparation products will be standard colon cleansing products approved by the FDA.

If necessary, capsule position will be monitored to ensure adequate booster administration. Subjects will keep a timed diary of key preparation steps and bowel activity, including capsule excretion. Subjects will be allowed to leave the unit only after the second boost was administered if the capsule is not yet excreted. Subjects leaving before excretion will be instructed to disconnect the recorder at excretion or 12 hours after capsule ingestion (whichever comes first).

#### Colon Preparation Procedure for Subjects Randomized to the CCE arm

Two Days Prior to the Procedure Day	Instructions
All Day	Drink at least 10 glasses of liquid
Bedtime	Four Senna tablets
The Day Before the Procedure Day	
Meals	Clear liquid diet all day
7:00pm – 9:00pm	2 liters sulfate-free PEG electrolyte lavage solution (such as ELS; NuLYTELY, Braintree Laboratories, Braintree, MA), one 8-10 oz. cup every 10-15 minutes.
Procedure Day	
Meals	None until 2 hours after suppository
45-75 min prior to capsule ingestion	2 liters sulfate-free PEG-ELS
	Capsule Ingestion
1 hour after capsule ingestion	Prokinetics (only if capsule is in stomach >1 hr.): 10 mg Metoclopramide (Reglan/Pramin) or 250 mg oral Erythromycin
First Boost: After capsule entry into small bowel	3 oz. SUPREP* plus 60 ml Gastrografin
Second Boost: 3 hrs. after first boost, only if capsule not excreted	3 oz. SUPREP* plus 30 ml Gastrografin
Suppository: 2 hrs. after second boost, only if capsule not excreted	10 mg Bisacodyl
2 hrs. after suppository	Standard full meal

\*Diluted in water per subject instructions form

**19.2 Appendix A2 – CCE Subject Instructions Form**

During the PillCam® COLON 2 procedure subjects will be asked to use a Subject Instructions Form to document their activities during the bowel preparation and colon capsule examination. This form will be used to document the subject's adherence to the procedure steps. The Subject Instructions Form will also serve as source data for CRF entries.

See attached document, "TOPAZ CCE Subject Instructions"

### 19.3 Appendix A3 – CCE Procedure Instructions

On the day of the examination, the arrival time of the subject at the clinic will be documented on the Subject Instructions Form (see Appendix A2) and the subject will complete the bowel preparation procedure as detailed in Appendix A1.

The subject's last bowel movement should be clear prior to beginning the CCE exam.

Between 45 and 75 minutes after the final PEG ingestion, the subject will swallow the PillCam® COLON Capsule with a cup of water.

Throughout the CCE procedure the subject will be instructed to verify when the capsule has exited the body and to inform the physician or the clinical coordinator of the time of exit. The time of exit should be documented on the subject instructions form and in the eCRF.

The PillCam Recorder will be disconnected either upon capsule excretion or DR alert "End of Procedure" (whichever comes first). If subject cannot be monitored for the entire procedure duration in the clinic, the subject may leave the clinic after administering the second boost while still connected to the system. The subject will be requested to disconnect the system at home upon one of the following: capsule excretion, "End of Procedure" alert or 12 hours from ingestion, whichever comes first, and send it back to the clinic the following day. The PillCam Recorder may also be removed in case of procedure failure.

Throughout the CCE procedure, the subject will be instructed to notify the study physician if experiencing abdominal pain, headache, vomiting, or any other unexpected symptoms.

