### **8.6.3 Radiologists**

Radiologists associated with each site will collaborate with the site principal investigator (gastroenterologist) to conduct the CTC examination. The radiologist can be assigned from a remote site. Experience and training are required in order to accurately perform CTC examinations, as defined in the ACR-SAR-SCBT-MR Practice Parameter for the Performance of Computed Tomography Colonography in Adults, Section III, Qualifications and Responsibilities of Personnel (23). In accordance with the practice parameters, radiologists meeting the qualifications will have, “substantial knowledge of radiation biology, the physics of CT scanning, the principles of CT image acquisition and postprocessing, including the use of diagnostic workstations, and the design of CT protocols, including rate and timing of contrast administration. The physician also will have substantial experience in CT interpretation, including CT of extracolonic structures that will be included on the CTC examination.” Education regarding patient preparation, bowel insufflation, and CT image acquisition as well as formal hands-on training are also required in accordance with the practice parameters, including “the interpretation, reporting, and/or supervised review of at least 50 endoscopically confirmed CTC cases.” The CTC exam sites will also be

expected to possess expertise in patient preparation, bowel insufflation, and CT image acquisition. Refer to the ACR-SAR-SCBT-MR Practice Parameters for additional details (23).

ACR-SAR-SCBT-MR Practice Parameter certification is required prior to reading CTC study cases.

Each radiologist participating in the clinical trial and the associated clinical study staff will receive training on the clinical protocol.

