#### 9.4 Safety Analysis

Individual listings of AEs, including type of device, AEs (reported term) start date, duration, severity, and procedure-relatedness will be provided. Procedure relatedness will be assessed separately relative to the imaging modality and colonoscopy, as described in Section 11.8.

AEs will be summarized using frequency counts and percentages. Descriptive statistics will be provided by study arm and by severity and relationship, according to the definitions in Section 11.8. Comparisons between treatments of the proportions of subjects experiencing at least one AE, at least one SAE, at least one CCE/CTC device/procedure related AE, and at least one colonoscopy procedure related AE will be made using Chi-square test or Fisher's exact test as appropriate.

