**20.2 Appendix B2 – CTC Subject Instructions Form**

Subjects randomized to the CTC arm will be provided with a subject instructions form that details the bowel preparation procedure described above. This form will be used to document the subject's adherence to the procedure steps and will also serve as source data for CRF entries.

See attached document, "TOPAZ CTC Subject Instructions"

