### 20.3 Appendix B3 – CTC Procedure Instructions

The subjects last bowel movement should be clear prior to beginning the CTC exam.

The CTC procedure and study interpretation will be conducted in accordance with the ACR–SAR–SCBT-MR Practice Parameter for the Performance of CT Colonography in Adults (Available from: <http://www.acr.org/quality-safety/standards-guidelines/practice-guidelines-by-modality/ct>) and other published literature (Johnson et al. N Engl J Med 2008;359:1207-17).

CTC examinations will occur at designated facilities with expertise in CTC procedures. ACR-SAR-SCBT-MR Practice Parameter certification is required prior to reading CTC study cases.

For CTC, colon insufflation will be performed with the subject in the lateral decubitus or supine position after placement of a catheter tip (with a retention balloon) in the rectum using an automated CO2 insufflator. The colon will be insufflated to a set pressure, which will likely require at least 2 liters of CO2.

The catheter will be left in the rectum, and, with the subject in the supine position, a CT scout image will be taken to confirm adequate colon distention. If adequate bowel distention is not achieved, additional air will be insufflated into the colon.

After scanning the subject in the supine position, the subject will be placed in the prone position, and additional CO2 will be administered. Subsequently, CT will be performed with the subject in the prone position. If a prone position is not possible for the subject, a right lateral decubitus position is preferred for optimal gas and fluid redistribution.

A low-dose technique without IV contrast administration or glucagon will be utilized.

Specific CT parameters include:

- 16 slice or greater MDCT
- Collimation: 0.5–1.0 mm
- Reconstructed slice thicknesses: 1–1.25 mm
- Reconstruction interval: 0.8 mm
- Pitch: 0.98–1.5
- Matrix: 512 × 512
- Field-of-view: to fit the subject
- 50 effective mAs
- Peak voltage: 120 kV
- Each series should be obtained in end expiration to minimize pressure effects of inflated lungs on the transverse colon

\*In case different CT machines are used, manufacture recommended protocol should be followed.

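### Only CCE subjects are told to report symptoms on the procedure day, which puts the between-arm AE tests at risk of unequal ascertainment

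*Combined protocol and SAP*

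**What the plan says.** **CCE arm.** Appendix A3 states that, throughout the CCE procedure, "the subject will be instructed to notify the study physician if experiencing abdominal pain, headache, vomiting, or any other unexpected symptoms". The subject may go home after the second boost with the recorder still connected, for up to 12 hours from ingestion.

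**CTC arm.** Appendix B3 opens with "The subjects last bowel movement should be clear prior to beginning the CTC exam" and then deals with insufflation, positioning and scan settings. It contains no instruction to report symptoms, and neither do Appendices B1 and B2. On location, it says "CTC examinations will occur at designated facilities with expertise in CTC procedures".

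**Both arms.** Sections 8.5 and 11.10 set one AE window, from the start of the CCE/CTC preparation to the call after colonoscopy. Table 2 lists AEs at Visit 2 and at the follow-up calls. Section 8.0 provides a call 5–9 days after CCE or CTC to capture any AE. No section says who asks about AEs at Visit 2, when, or with what questions.

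**Exclusion.** Section 11.10 lists occurrences expected after bowel preparation that are not reportable unless serious. Vomiting, headache and abdominal pain are among them.

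**Analysis.** Section 9.4 compares the arms on the proportions with any AE and any SAE, and continues: "at least one CCE/CTC device/procedure related AE, and at least one colonoscopy procedure related AE will be made using Chi-square test or Fisher's exact test". It states no significance level, power or success rule for these tests. Section 8.10.3 says that neither subject nor investigator is blinded to the arm.

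**The concern.** A test of AE proportions is interpretable only if an event of a given kind has about the same chance of being recorded in each arm. Here the only written procedure-day elicitation belongs to one arm. A common rule on what to collect is not a common method of asking, and in an unblinded trial nothing else equalises the asking.

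The events most sensitive to prompting are brief and mild ones. The protocol expects such events with CTC: section 6.1 attributes subjects' preference for CCE in the earlier head-to-head study to bloating and mild pain during CTC, and Table 1 lists mild, self-limiting abdominal pain among that study's CTC findings. If these effects are not asked about on the day, they depend on spontaneous report or on recall at the call. The tested difference would then combine true risk with solicitation, and symptoms that nobody asked about cannot be recovered at analysis.

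**Working it through.** The plan gives no AE rate, capture rate or power for the safety tests, so there is no figure to reproduce. The check has two parts.

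**1. The texts side by side**

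| Element | CCE | CTC |
|---|---|---|
| Procedure-day instruction to report symptoms | Yes (A3) | None (B1–B3) |
| AE window | Same (8.5, 11.10) | Same |
| AE collection at Visit 2 | Yes (Table 2), method not stated | Yes (Table 2), method not stated |
| Call at 5–9 days | Yes (8.0) | Yes (8.0) |
| Preparation products on the procedure day | Yes: PEG before ingestion, then boosts (A1) | None listed; last item is at 8 pm the day before (B1) |

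The difference is therefore one extra prompt in the CCE arm on top of shared collection. The last row bears on direction. A CCE symptom during the examination can readily be put down to preparation and so fall under the 11.10 exclusion. Discomfort during CTC insufflation is less easily attributed that way, and section 11.0 asks for all CTC-related AEs. The prompt would raise CCE counts and the exclusion would lower them, so the net sign cannot be read from the text.

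**2. How much unequal capture would matter (illustration)**

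Inputs:
- 160 per arm at maximum and about 10% attrition (section 9.1): 160 × 0.9 = 144 per arm.
- Assumed: true AE proportion π, equal in the two arms; full capture in one arm; capture c in the other.
- Assumed: two-sided 5% test, by Pearson chi-square, or Fisher where an expected count is below 5.

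Observed proportions are π and cπ, so the spurious difference is π(1 − c). Exact binomial enumeration gives the chance of a false significant result:

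| True π | c = 100% | c = 90% | c = 75% | c = 50% |
|---|---|---|---|---|
| 5% | 4.7% | 5.0% | 7.2% | 16.7% |
| 10% | 4.9% | 5.8% | 11.2% | 35.5% |
| 20% | 5.0% | 7.2% | 20.1% | 67.3% |
| 30% | 5.0% | 8.8% | 30.7% | 87.1% |

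Hand check of π = 20%, c = 75%:
- Observed 20% v 15%, difference 0.05, pooled proportion 0.175.
- SE = √(0.175 × 0.825 × 2/144) = 0.0448, so z = 0.05/0.0448 = 1.117.
- Φ(1.117 − 1.960) = Φ(−0.843) ≈ 0.20, in agreement with the exact 20.1%.

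With equal arm sizes the table is the same whichever arm loses events. At c = 90% the false-positive chance stays between 5.0% and 8.8%. It becomes material only when capture differs substantially.

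**The case against.** The strongest reply is that AEs are collected in both arms at Visit 2 and at the same call, under one rule covering every AE whatever its severity or relationship. On that view A3 is a supervision measure for subjects who may go home still connected to a recorder, whereas insufflation and scanning are done by staff who are present. The three symptoms that A3 names are also on the 11.10 list, so much of what the prompt elicits may never enter the tests. All of this stands, and it limits the point to a risk. It does not remove the point: Visit 2 collection has no stated method, A3 also asks for any other unexpected symptom, and 11.10 does not clearly cover insufflation effects.

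A reader might infer more than the documents support:

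- *That harms are in fact ascertained unequally.* Shared collection may be nearly complete, and the documents do not say.
- *That the CCE diary and form add to the asymmetry.* The diary is described thus: "Subjects will keep a timed diary of key preparation steps and bowel activity, including capsule excretion". The CCE form is to "document their activities during the bowel preparation and colon capsule examination". For CTC, "Subjects randomized to the CTC arm will be provided with a subject instructions form that details the bowel preparation procedure described above". These record steps, bowel activity and adherence; none is described as collecting symptoms. The attached forms are not in the documents, so their fields cannot be judged.
- *That CT staff are less trained in AE reporting or out of reach.* Section 8.6.1 names AE reporting as part of protocol training. Section 8.6.3 gives radiologists and staff training on the same protocol, and shorter wording is not evidence of less training. "The radiologist can be assigned from a remote site" concerns the radiologist, not the absence of study staff.
- *That the head-to-head study fixes the size.* Its CTC counts (2 with significant pain, 10 with mild pain, among 50) cannot serve as an equal risk for both arms, because it reports no CCE AEs associated with procedure or preparation and only 2 subjects with difficulty swallowing. If risks truly differ that way, missed CTC events would shrink a real difference rather than create a false one.

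**Conclusion.** The point holds as a risk of differential ascertainment. The procedure-day prompt is written for CCE only, no common method of elicitation is set for Visit 2, the trial is unblinded, and section 9.4 tests AE proportions between the arms. Brief CTC procedure effects are the most exposed.

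Size and net direction are unknown. The illustration assumes equal true risk, complete capture in one arm and the maximum sample after attrition; its capture rates are not from the documents. If shared capture is nearly complete, the effect is negligible.

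The stakes are modest: this is a safety comparison without a success rule, and the primary endpoint is untouched. The change is still worth making, because it is cheap and the loss cannot be repaired afterwards.

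**What to change.** 1. Add to Appendix B3 a sentence that matches A3: the same symptoms, the same open-ended item and the same person to notify. State one common end time for the instruction in A3 and B3.
2. In sections 8.10.5 and 11.10 and in Table 2, specify one short symptom query, identical in both arms. Gastroenterology site staff put it to the subject at the end of Visit 2 (by telephone if the CT facility is remote) and again at the 5–9 day call.
3. In section 9.4, state that the between-arm AE comparisons draw on these common sources. Events learned of in other ways, and all serious events, are still recorded and listed.

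Keep the A3 instruction: the remedy adds an equivalent for CTC and takes nothing from CCE. The cost is a sentence in B3, a line in A3, a short form and a few minutes of existing staff time per subject. The downside is that a few more minor events will be recorded.
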